The rationale for the duration of the interventions, follow up, and blinding procedures: The proposed study is of standard duration for the geriatric population requiring 12 weeks or longer trials to document antidepressant efficacy.

4.0 *Research Design and Methods: Describe in detail the design and methodology of the study.

Subjects: We anticipate screening about 100 subjects to recruit 60 older depressed adults (>60 y.o.) who will be randomized to receive 20-120 mg of levomilnacipran blindly with increment dose titration 20 mg per day -3 days; 40 mg per day-3 days. Based on efficacy and tolerability, we will increase by 40 mg per day each following week 2nd-4th week the maximum recommended doses is 120 mg per day. The comparison group will receive similar blinded titration with matching placebo. Doses of the drugs will be adjusted according to individual tolerability and safety. We expect an attrition rate of about 10% based on our prior experience thus 54 subjects will complete the study. Patients will be assessed pre-treatment; and then weekly during the first four weeks and bi-weekly thereafter. At all visits, clinical ratings of mood, vital signs, and safety will be obtained. Inclusion criteria: 1) The presence of a major depressive disorder diagnosed according to the DSM-IV criteria. 2) A 24-item Hamilton Rating Scale for Depression (HAMD) score of 17 or higher at baseline. 3) Mini-Mental State Exam (MMSE) score > 24.

Exclusion criteria: subjects will be excluded if they had 1) any current and/or lifetime history of other psychiatric disorders (except unipolar depression with or without comorbid generalized anxiety disorder), or 2) recent unstable medical or neurological disorders; 3) any disabilities preventing their participation in the study or in the MRI; 4) diagnosis of dementia; 5) acute suicidality; 6) those with known allergic reactions to milnacipran, uncontrolled narrow angle glaucoma, seizures, poorly-controlled hypertension or ischemic changes on ECG, serotonin syndrome, or the recently used MAOIs within last 4 weeks; 7) ineligible for MRI (e.g., metal in the body or claustrophobia)

Primary outcome will be measured and defined as follows: 1) Remission will be defined as HAMD scores of 6 or less for three consecutive weeks and at week 12; 2) Improvement in depression severity using HAMD scores.

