Neuropsychological assessment (at baseline, at 12 weeks): Our approach to cognitive assessment and analyses is based on our prior work and benefits from input from [name]. We will use a focused test battery developed by [name], assessing domains which have shown impairment in geriatric depression, according to prior research by our group45 and others: 9,46-48 (1) cognitive control, which relates to mental flexibility and inhibition and adjustment of behavior; (2) verbal fluency, which requires strategic searching/organization of verbal knowledge; (3) episodic memory: including explicit memory for verbal and nonverbal information; and (4) information processing speed and attention, including an indices of complex and sustained attention. Most of the measures have 2 or 4 alternate forms that will be important in repeating them during follow up. In addition to the cognitive outcome measures, we will include a brief word reading test, the WAIS-IV Test of Premorbid Functioning (TOPF), a revision of the Wechsler Test of Adult Reading (WTAR),49 to estimate an individual premorbid cognitive functioning. We will conduct a confirmatory factor analysis to assess the goodness of fit of our a priori domain assignments. Finally, we will assess the validity of assignment to composite domains using confirmatory factor analysis. The tests variables derived from each and a priori composite domain assignment: Verbal Fluency (Category and Letter Fluency tests): Cognitive Control (Trailmaking test part B and Stroop Color-Word Interference test); Attention and Processing Speed (Trailmaking test part A; Stroop rapid color and word reading scores (averaged); Digit vigilance d-prime); and Episodic Memory (Rey Auditory Verbal Learning; Brief Visual Spatial Memory tests).

Safety evaluations. Physical examination and vital signs at baseline: pulse rate, systolic blood pressure, and body weight will be obtained at each visit, in addition to a 12-lead ECG at baseline, if any cardiac complaints are present. Laboratory tests (as listed below) will be performed at baseline. The UKU Side Effect Rating Scale,50 a comprehensive rating scale for monitoring adverse events of psychotropic drugs used in clinical trials, will be completed at all visits except screening.

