Hypothesis 1: The primary analyses will focus upon HAM-D24 scores and will be analyzed using general linear mixed model analysis (e.g., SAS PROC MIXED). The two treatment groups will be compared for time course of HAM-D-24 with the initial endpoint EOT at 12 weeks. Covariates may be included in the model as noted above. In addition, likelihood ratio ?2 comparison will examine group differences in remission (HAM-D24 =6) and response (HAM-D24 =10) at EOT. Analyses for the cognitive outcome variables will be akin to those described above for the continuous HAM-D scores. As noted in the Neuropsychological Assessment section, there are four cognitive domains that are being assessed. Of these, the two primary cognitive domains of interest for this proposal are Cognitive Control and Episodic Memory. A separate general linear mixed model as above will be estimated using these two domain scores as dependent variables. The remaining domains, namely Verbal Fluency and Information Processing/Attention will be examined as secondary outcome measures. Apathy will be examined using the AES total score and quality of life using SF-36 scores in similar mixed models.

Hypothesis 2: We will examine adverse events in the two treatment groups. A detailed comparison of the number as well as type of side-effects in the two treatment groups will be conducted using chi-square tests.

Hypothesis 3: LMIL will lead to improved functional connectivity in brain network activity as measured with resting state (rs-) fMRI, and plasticity in brain macro- and micro-structure as measured with structural MRI and DTI compared to the PBO. To address these hypothesis, summary MRI measures (e.g., substructure volume, diffusion metrics) will be included in the GLMMs as "covariates of interest." For whole brain or structure voxel-level or point based measures (e.g., thickness or activation), the GLMMs will be implemented in R (www. R.org). Time (of scan) will be treated as a continuous variable with random intercepts and slopes to account for within-subject correlations between repeated measurements to assess change and interactions amongst the interventions. Difference scores between baseline and 12-week follow-up may be substituted for some analyses. FDR and/or permutation methods will be used to control for multiple anatomic comparisons in whole-brain contexts.

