Hypothesis 4: The role of brain neuroimaging biomarkers in variability of treatment response is examined in this Hypothesis. Predictor variables: We predict that baseline measures of neuroimaging biomarkers of emotional responsivity; working memory and connectivity will be related to treatment outcomes. These predictions will be evaluated in the context of the models described above (i.e., general linear mixed model) by adding the posited prognostic variable as an additional predictor.

Power. With a significance level (alpha) of 0.05, 80% power, and N = 30 in each treatment arm, we can detect an effect size (ES, difference between group means as a multiple of the standard deviation) of 0.7. Using appropriate covariates such as age of onset, chronicity, and number of episodes can be expected to reduce variance and increase power for a given difference in mean, hence the two-sample power computations are conservative for this situation. This study will thus yield sufficient pilot data to justify conducting a larger study in the future.

Data management. Data management and analysis support will be provided by the UCLA SI-STAT services and [name] will supervise the data gathering duties of the study coordinator, including reviewing all data entry forms. 1. Randomization. The prestudy forms must be submitted before a patient can be randomized. A separate portion of the database will also be maintained for patients screened but not enrolled or randomized. Randomization schedules will be prepared in a masked manner by the statistician. 2. Data submission and quality control. Data forms will be delivered from the originating location to the central data unit within one week of being generated. When errors, omissions, or unclear information is detected on the paper forms, a copy

will be returned for corrections. The data manager will generate monthly reports summarizing missing and incorrect data will be sent to the PI. 3. Data confidentiality. Patient study forms will be stored in locked file cabinets and will be accessible only to authorized personnel. A shredder will be used to discard all unwanted study documents. Access to the data will be password protected with only authorized persons having knowledge of the password.

ID: IRB#14-001827

View: NEW 11.1 - Characteristics of the Study Population

Warning: Save your work at least every 15 minutes by clicking \$Save\$ or \$Continue.

Characteristics of the Study Population

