Mild Cognitive Impairment diagnosis. Subjects with mild cognitive impairment will not be excluded. We will use performances between -1.5 and -2 (SD) below age and education norms on one of two memory tests used in our cognitive battery according to a widely accepted practice, and control for it in the analyses.

Randomization and treatment schedule: After all screening and baseline test results are reviewed and eligibility criteria are confirmed by [name]., medications will be dispensed if patients continue to meet eligibility criteria and sign the informed consent form. All eligible subjects will be randomized to levomilnacipran or placebo group using a computer-generated random assignment scheme, which assigned subjects in a 1:1 ratio to each group. Randomization will be done prior to subject sbeing assigned to the groups.

Monitoring of Suicidality.

Assessment and monitoring of suicidal risk will occur at each visit and by phone between visits. We have applied the standard procedures that are required and approved by the UCLA Institutional Review Board. We have employed the same procedures in our ongoing studies of late-life depression since 1995, and have had no suicide attempts among our subjects. We will monitor suicidal ideations using the third item of the Hamilton Depression Scale during each visit to the site. Monitoring for SI will be done at each visit independent of the outcome assessment. The blind rater will be instructed to inform the PI of scores = 3. Subjects with active suicidal ideations with or without a plan, HAMD-24 score = 3, will be excluded from participation. We will call subjects between visits to monitor suicidal ideations. We will encourage participation of their family members in the study who will be encouraged to call the patient and the study staff in case suicidal ideations emerge during the study. In the presence of persistent suicidal ideations, subjects will be discontinued from the study and referred to clinical services or to the community for treatment.

ID: IRB#14-001827

View: NEW 11.2 - Characteristics of Study Population

Warning: Save your work at least every 15 minutes by clicking & Save & or & Continue.

7	k all that apply: 0 to 6 years 7 to 11 years 12 to 17 years
7	7 to 11 years
	·
	12 to 17 years
	12 to 17 years
	17 or younger in California who can consent for themselves - see note below
	17 or younger outside California who can consent for themselves - see note below
*	18 years or older
4	
NOTE	=.

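### The cognitive models name no baseline score as covariate, only an MCI flag that does little; adjusting for the continuous baseline score already collected would give a modest gain in precision

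*Combined protocol and SAP*

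**What the plan says.** All references are to the combined protocol and SAP.

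- **MCI flag.** Sections 10.1 item 4.0 and 11.1 item 6.0 (Mild Cognitive Impairment diagnosis) admit patients with MCI. The condition is identified by a score band, −1.5 to −2 SD relative to norms for age and education. The plan applies this band "on one of two memory tests used in our cognitive battery according to a widely accepted practice, and control for it in the analyses". No particular outcome is named.
- **Memory tests.** Section 10.1 item 4.0 (Neuropsychological assessment) gives the battery at baseline and week 12 and lists the domain "Episodic Memory (Rey Auditory Verbal Learning; Brief Visual Spatial Memory tests". No other memory tests are listed.
- **Status.** Section 10.1 item 6.0 (Hypothesis 1) says "the two primary cognitive domains of interest for this proposal are Cognitive Control and Episodic Memory". The Specific Aims (section 10.1 item 2.0) class cognition as secondary to mood.
- **Model.** The same Hypothesis 1 paragraph analyses cognition like HAM-D: a mixed model comparing the arms' course over time. Covariates are optional. Those named in item 6.0 are demographic or describe the course of depression. A baseline cognitive score is not among them.
- **Size.** The Power paragraph states: "With a significance level (alpha) of 0.05, 80% power, and N = 30 in each treatment arm", and continues: "we can detect an effect size (ES, difference between group means as a multiple of the standard deviation) of 0.7". Section 10.1 item 4.0 adds: "We expect an attrition rate of about 10% based on our prior experience thus 54 subjects will complete the study".

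**The concern.** A baseline measurement of the outcome is usually its strongest predictor, and here it costs nothing because every patient has the tests at baseline. The plan never says how that score enters the cognitive models. What it does promise is control for MCI. For Episodic Memory this is very probably a yes/no version of the outcome's own baseline, and a yes/no version keeps only part of the information.

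If baseline is instead a response in the mixed model, the flag does almost nothing and the treatment contrast is a change score. A change score is never more precise than baseline adjustment. At stake is the precision of the cognitive effect estimates in about 54 completers, in a pilot whose primary aim includes estimating effect sizes.

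**Working it through.** **1. The plan's own figure.** Alpha is 0.05. Sidedness is not stated, so I take it as two-sided. Power is 80% with 30 per arm. The detectable effect is (1.960 + 0.842) × √(2/30) = 0.723 SD by the normal approximation, or 0.736 by the t distribution. Both print as 0.7. Taken as exactly 0.7, power is 77.4% (normal) or 76.0% (t). Rounding explains the gap, so I do not treat the stated figure as wrong.

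**2. Completers.** 60 × 0.9 = 54, or 27 per arm at 1:1.

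**3. Variance of the treatment contrast.** Take the week-12 SD as 1, the same SD at baseline, and the same rho in both arms. The per-patient variance factor is:

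- week 12 only: 1
- week 12 with the MCI flag: 1 − rho² × R², where R² is the share of the baseline composite's variance that the flag captures
- baseline and week 12 as responses with group-by-time (equivalent to change, with complete data): 2(1 − rho)
- continuous baseline as covariate, or a common baseline mean: 1 − rho²

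The ratio of the last two is 2(1 − rho)/(1 − rho²) = 2/(1 + rho): 1.25, 1.18 and 1.11 at rho 0.6, 0.7 and 0.8. In standard error this is about 12, 8 and 5%.

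**4. Why the flag drops out.** A main effect of a baseline characteristic shifts a patient's baseline and week-12 values equally, so it cancels from the difference. Entering it with its own time effect changes little. In simulation (30 per arm, 0.7 SD, rho 0.7, the flag as the plan defines it), power was 92.6% for change, 92.3% for change with the flag, and 95.5% for the continuous baseline.

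**5. Power, two-sided, 27 per arm.** This uses the noncentral t with noncentrality d × √(27/2) / √(variance factor), and one degree of freedom spent on the covariate.

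| Effect | Model | rho 0.6 | rho 0.7 | rho 0.8 |
|---|---|---|---|---|
| 0.5 SD | change | 52.2% | 64.3% | 81.3% |
| 0.5 SD | continuous baseline | 61.5% | 71.4% | 85.2% |
| 0.7 SD | change | 80.6% | 90.3% | 97.9% |
| 0.7 SD | continuous baseline | 88.4% | 94.2% | 98.8% |

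Example: at 0.5 SD and rho 0.6 the noncentrality is 0.5 × 3.674/√0.8 = 2.05 for change and 0.5 × 3.674/√0.64 = 2.30 for baseline adjustment. Chance baseline imbalance takes up to about one point off the adjusted rows, so I quote 61.5% as about 61%. The gain is about 4 to 9 points at 0.5 SD and 1 to 8 points at 0.7 SD. At rho 0.3 it is larger: 33% against 47% for 0.5 SD.

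**6. How much the flag keeps.** I assume a correlation between the two memory tests of 0.3 to 0.7 and a sample mean 0 to 0.5 SD below norms. The flag as the plan defines it then captures R² = 0.17 to 0.24 of the baseline composite. With the mean as low as 1 SD below norms, the range widens to 0.12 to 0.24. A flag for everyone at or below −1.5 SD captures 0.30 to 0.59 over that wider range. With R² of 0.17 to 0.24, a week-12-only model with the flag has 46 to 50% power for 0.5 SD at rho 0.6 to 0.8. Without any adjustment it has 44%.

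**The case against.** The strongest case against is that the plan does not make the flag a substitute for the baseline score. It controls for a diagnosis in its analyses generally. Cognition is measured only twice, so a mixed model of its course over time needs the baseline value as a response. On that reading the continuous baseline is already in the analysis and the flag does no harm. No model is biased: in simulation with no treatment effect, every model rejected in 4.3 to 4.9% of trials. Cognition is also a secondary outcome in a pilot, and rho, the inter-test correlation and the MCI prevalence are all assumptions.

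Most of this stands. A reader might infer that the flag is the only baseline information in the Episodic Memory analysis, so that the fix would lift power for 0.5 SD from 46–50% to about 61–85%. The documents do not support that as a description of the plan, because it needs a week-12-only model that section 10.1 item 6.0 does not describe. The fair comparator is change from baseline.

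A reader might also infer that the flag should go from every cognitive model. That does not follow either. In the other three domains it is not a recode of the outcome's own baseline.

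What the objection does not remove is that an unconstrained group-by-time model is less precise than baseline adjustment at any rho below 1, and nothing in the plan says that the arms share a baseline mean.

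**Conclusion.** The point holds as a modest, nearly free gain in precision on a secondary outcome. It is not a bias or an invalid test. On the natural reading, the cognitive treatment contrast carries 11 to 25% more variance than baseline adjustment at rho 0.8 to 0.6, and the MCI control contributes almost nothing to it. The gain is larger if rho is lower or if the model uses week 12 only with the flag. It is nil if the model already constrains the arms to a common baseline mean.

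The sizes rest on an assumed rho, equal variances at the two visits, complete data in 27 patients per arm, and two-sided testing. That the two MCI tests are the Episodic Memory pair is a strong inference, since the battery lists no others, but the plan does not state it. The variance comparison in all four domains does not depend on that inference.

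**What to change.** Add one sentence to section 10.1 item 6.0 (Hypothesis 1). In each of the four cognitive domain models, the week-12 comparison is adjusted for the continuous baseline score of that domain; alternatively, baseline stays as a response and the arms are constrained to a common baseline mean. In the Episodic Memory model, do not rely on the MCI flag as the baseline adjustment. It may remain as an optional covariate there and in the other analyses.

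The cost is at most one degree of freedom per model and the wording. The baseline scores are already collected, so no visit, test or sample size changes.
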